3. STUDY DESIGN

3.1. Overall Design

[figure not shown]
This Phase 2, multicenter, randomized, double-blind, placebo-controlled study in adult subjects with moderate-to-severe AD whose disease is not adequately controlled with topical therapies, or for whom those therapies are not advisable, is designed to evaluate the safety and efficacy of etrasimod monotherapy compared with placebo. The study includes multiple periods: up to a 4-week Screening Period (to determine subject eligibility); a 12-week Double-Blind Treatment Period with a 4-week Safety Follow-Up Period following the last dose of double-blinded study treatment; and eligible subjects may enter a 52-week Open-Label Extension Period also followed by a 4-week Safety Follow-Up Period after the last dose of study treatment (Figure 1). Subjects with chronic AD defined by Hanifin and Rajka criteria () that has been present for at least 1 year despite optimized skin care (ie, use of emollients, avoidance of irritants) will be equally randomized (1:1:1 ratio) to receive etrasimod 1 or 2 mg or placebo.

Randomization will be stratified by validated Investigator’s Global Assessment (vIGA) score at Baseline (3 versus 4) and region (as appropriate). Subjects will receive etrasimod 1 or 2 mg or placebo orally once daily in a double-blind manner for 12 weeks. During the Open-Label Extension Period, all eligible subjects will receive etrasimod 2 mg orally, once daily. The application of topical moisturizers will be required at least once daily for at least 1 week prior to randomization and throughout the study without change (ie, type, frequency, application).

Rescue therapy will be permitted for uncontrolled symptoms at the discretion of the investigator based on an exacerbation of disease severity or subject self-reporting of worsened symptoms.

Figure 1: Study Design

D, day; PO, oral; QD, once daily; W, week

3.2. Discussion and Rationale for Study Design

This Phase 2 study will be a randomized, double-blind, placebo-controlled, efficacy and safety study that is intended to support the development of etrasimod for the treatment of moderate-to-severe AD. The subjects will be those with moderate-to-severe AD whose disease cannot be adequately controlled with topical medications, or for whom topical treatment is medically inadvisable despite optimized skin care.

This study will assess etrasimod monotherapy compared to placebo. The choice of placebo as a control is appropriate for the objectives of this study since it will provide the most robust assessment of the efficacy and safety of etrasimod. The 12-week treatment duration was selected to ensure that etrasimod could reach its maximal efficacy with some maintenance of effect while minimizing the time that a subject may be on placebo treatment. As this is a placebo-controlled study, the duration is limited, although rescue therapy is permitted for intractable symptoms, at the investigator's discretion. Regardless of the dose or treatment to which subjects are randomized in the Double-Blind Treatment Period, eligible subjects may continue into the Open-Label Extension Period with etrasimod 2 mg once daily for up to 52 weeks if continuation eligibility criteria are fulfilled. The Open-Label Extension is designed to allow subjects to continue etrasimod therapy and to assess long-term safety and tolerability of 2 mg once daily dosing as a chronic therapy.

Efficacy will be evaluated by changes in AD severity using the Eczema Area and Severity Index (EASI), vIGA, SCORing Atopic Dermatitis (SCORAD), and affected body surface area (BSA). To best understand the potential dose-dependent efficacy of etrasimod, the primary endpoint will be the percent change in EASI from Baseline to end of the Double-Blind Treatment Period (Week 12).

Additionally, because patient-reported outcomes (PROs) can provide subject perspectives on aspects of their disease conditions and overall health status, several PROs will be explored in this study. The pruritus numeric rating scale (NRS) will be collected by each subject on a daily basis and recorded in a diary with a 24-hour recall period. The pruritus NRS may also be assessed at the study visits. To capture important symptoms of AD and subject responses to therapy, other well used instruments such as the Patient Global Assessment (PGA), Dermatology Life Quality Index (DLQI), and Patient Oriented Eczema Measure (POEM) will be assessed at study visits. Sleep and itch will also be monitored as part of the SCORAD.

3.3. End of Study

Primary Completion: The date on which the last subject was examined or received an intervention to collect final data for the primary endpoint. In this study, this date is defined as when the last subject has completed assessments for Week 12.

End of Study: The end of the study is defined as the date of the last visit of the last subject in the study globally.

4. STUDY POPULATION

4.1. Inclusion Criteria – Double-Blind Treatment Period

Subjects must meet ALL of the following inclusion criteria to be eligible for enrollment into the study:

1. Men or women between ≥ 18 and ≤ 70 years of age at the time of informed consent.
2. Chronic AD, defined by Hanifin and Rajka criteria ([REDACTED]), that has been present for at least 1 year prior to the Screening Visit.
3. EASI ≥ 12 at the Screening Visit and ≥ 16 at the Baseline Visit.
4. vIGA score ≥ 3 (on the 0 to 4 vIGA scale, in which 3 = moderate and 4 = severe) involvement at the Screening and Baseline visits.
5. BSA $\geq 10\%$ of AD involvement at the Screening and Baseline visits.
6. Recent history (within 6 months prior to the Screening Visit) of inadequate response to treatment with topical medications, or when topical treatments are otherwise medically inadvisable (eg, because of important side effects or safety risks), which can be documented by medical records or by the history provided to the investigator by the subject despite optimized skin care (ie, avoidance of irritants, use of emollients).
7. Willing to apply a dose of topical emollient/moisturizer at least once daily for ≥ 1 week prior to the Baseline Visit and willing to continue daily application over the course of the study without change (ie, type, frequency, application).
8. Willing and able to comply with all clinic visits and study-related procedures and understand and complete study-related questionnaires.
9. Provide signed informed consent prior to conducting any procedures.

4.2. Exclusion Criteria – Double-Blind Treatment Period

Subjects will be excluded from the study if they meet ANY of the following exclusion criteria.

[REDACTED]

[REDACTED]

[REDACTED]

[REDACTED]

[REDACTED]

[REDACTED]

[REDACTED]

[REDACTED]

[REDACTED]

[REDACTED]

[REDACTED]

[REDACTED]

3. Phototherapy for AD or artificial tanning (beds, booths, or lamps) within 4 weeks prior to Screening or during Screening.
4. Presence of skin comorbidities that will interfere with study assessments of the underlying disease.

[REDACTED]

[REDACTED]

[REDACTED]

[REDACTED]

[REDACTED]

[REDACTED]

[REDACTED]

[REDACTED]

[REDACTED]

[REDACTED]

[REDACTED]

[REDACTED]

[REDACTED]

[REDACTED]

[REDACTED]

[REDACTED]

[REDACTED]

[REDACTED]

[REDACTED]

[REDACTED]

[REDACTED]

[REDACTED]

[REDACTED]

[REDACTED]

[REDACTED]

[REDACTED]

[REDACTED]

[REDACTED]

[REDACTED]

[REDACTED]

[REDACTED]

- [REDACTED]
- [REDACTED]
- [REDACTED]

[REDACTED]

[REDACTED]

[REDACTED]

- [REDACTED]
- [REDACTED]

[REDACTED]

- [REDACTED]
- [REDACTED]
- [REDACTED]
- [REDACTED]
- [REDACTED]

[REDACTED]

[REDACTED]

[REDACTED]

[REDACTED]

[REDACTED]

[REDACTED]

[REDACTED]

[REDACTED]

[REDACTED]

[REDACTED]

[REDACTED]

[REDACTED]

5. SUBJECT ACTIVITIES AND RESTRICTIONS

For dosing requirements, including holding the dose prior to the study visit on study visit days, see Dosage and Administration, Section 6.3. Rescue therapies and prohibited medications/procedures are located in Section 6.8.2 and Section 6.8.3, respectively.

Optimized skin care is expected to be followed prior to and maintained throughout the study as per current guidelines and recommendations for AD (Eichenfield 2014, Eichenfield 2017). Subjects are expected to continue their usual skin care routine and basic skin care regimen without notable changes for the course of the study treatment and follow-up periods. This includes frequency and length of showering or bathing, including bleach baths, the use of emollients, topical anesthetics, antihistamines, and topical and systemic anti-infective medications.

Subjects must be willing to apply topical emollient or moisturizer at least once daily for ≥ 1 week prior to the Baseline Visit and willing to continue daily application over the course of the study without change (ie, type, frequency, application).

On visit days during the study, subjects should not apply any topical emollient or moisturizer prior to attending clinic and completing their visit. Study treatment should also be held the day of clinic visits. Subjects will take their daily dose at the study site on study visit days.

6. STUDY TREATMENT

Study treatments used in this study include the pharmaceutical form of the active substance being tested (test product) and the placebo being used as a reference.

6.1. Study Treatment(s) Administered

Study treatment(s) for the Double-Blind Treatment Period are listed in Table 1. During the Open-Label Extension Period, all eligible subjects will receive 2 mg etrasimod.

Table 1: Study Treatment(s)

Study Treatment	Dose	Mode of Administration	Frequency	Formulation
Etrasimod	1 mg	Oral	Once daily	Tablet
Etrasimod	2 mg	Oral	Once daily	Tablet
Placebo	NA	Oral	Once daily	Tablet

NA, not applicable

6.2. Identity of Study Treatment

6.2.1. Etrasimod

The active pharmaceutical ingredient in etrasimod tablets is APD334 [REDACTED]

[REDACTED] APD334 [REDACTED] is manufactured, packaged, tested, and released in compliance with current Good Manufacturing Practice.

Etrasimod tablet drug product is a blue, round, biconvex, plain, immediate-release, film-coated tablet. Etrasimod tablets are composed of APD334 [REDACTED]

[REDACTED] and is supplied in the dosage strength (based on etrasimod free acid content) of 1 and 2 mg.

6.2.2. Placebo

The placebo tablet formulation is composed of excipients [REDACTED]

[REDACTED] The placebo drug product is manufactured, packaged, tested, and released in compliance with current Good Manufacturing Practice.

6.3. Dosage and Administration

One tablet (etrasimod 1 or 2 mg or placebo) is to be taken once daily with water (either with or without food) at approximately the same time each day, preferably in the morning. On study visit days, subjects should wait to take their assigned dose until after [REDACTED] blood samples have been drawn and after all pre-dose assessments and procedures have been

completed. Subjects will take their daily dose at the study site on study visit days. The time of [REDACTED] sample collection and subsequent dosing should be documented.

6.3.1. Instructions for Missed Dose(s)

Subjects should be instructed that if they forget to take a dose, they can take the dose within 8 hours of the normal dosing time; otherwise, they should take their next dose at the regular time on the following day. If the subject vomits the tablet, he/she should be instructed not to take another tablet on the same day, but to take the next dose at the regular time on the following day. Subjects should be instructed to contact the investigator if they miss more than 2 consecutive doses.

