6.3.2. Dose Interruptions

If the investigator deems it necessary to withhold study treatment, temporary withholding is permitted for up to 3 days without obtaining prior approval from the Sponsor. If study treatment interruption ≥ 7 days is required for a medical reason, the investigator must contact the medical monitor as soon as this is anticipated.

The procedure for first-dose cardiac monitoring as outlined in Section 10.5.7.4 should be performed and/or discussed with the medical monitor any time a subject misses a study treatment as follows:

- ≥ 2 consecutive days within the first week of study treatment
- ≥ 7 consecutive days after the first week of study treatment

If these doses of study treatment are missed, subjects must contact the Investigator to discuss treatment re-initiation and are required to return to the study site before taking their next dose of study treatment. The subject must take the next dose of study treatment at the study site, and the in-clinic cardiac monitoring as outlined in Section 10.5.7.4 should be performed.

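### In the first week, the missed-dose call instruction in Protocol 6.3.1 starts one dose later than the mandatory contact and on-site restart in 6.3.2

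*Protocol*

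**What the plan says.** Protocol 6.3 sets the regimen. One tablet "is to be taken once daily with water", and "Subjects will take their daily dose at the study site on study visit days".

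Protocol 6.3.1 covers what subjects are told about missed doses. A forgotten dose may be taken up to 8 hours late; after that, the subject waits for the next day's usual dose. The section then gives its only trigger for a call: "Subjects should be instructed to contact the investigator if they miss more than 2 consecutive doses". It makes no distinction by week and does not refer to 6.3.2.

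Protocol 6.3.2 covers interruptions and has two thresholds: "≥ 2 consecutive days within the first week of study treatment" and "≥ 7 consecutive days after the first week of study treatment". Once either is met:

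- "subjects must contact the Investigator to discuss treatment re-initiation";
- they have to come back to the clinic first and may not simply resume at home;
- "The subject must take the next dose of study treatment at the study site".

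The wording on cardiac monitoring is softer. The lead-in says that it should be carried out, talked through with the medical monitor, or both, and the closing sentence also uses should.

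**The concern.** The duty to make contact in 6.3.2 falls on the subject. A site may not learn of missed home doses until the subject calls or attends, so the threshold that subjects are given matters. In the first week the figure in 6.3.1 is one dose higher than the one in 6.3.2. A subject counselled from 6.3.1 alone could miss two doses, see no reason to call, and take the third at home. Section 6.3.2 does not allow that.

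The precaution is the sponsor's own. Protocol 1.3 describes a fall in heart rate on first dosing as an expected class effect. It commits to direct observation after the Day 1 dose and when treatment is restarted after a defined interruption. The two-day threshold in 6.3.2 appears to put that into practice for the first week. What is at stake is a restart without contact or site attendance; no endpoint or analysis is involved.

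**Working it through.** The plan states no figure to reproduce. The check compares two threshold rules.

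**Inputs.** Let k be the number of consecutive missed doses. Dosing is once daily (6.3), so k doses equal k days.

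- 6.3.1, call: more than 2, so k ≥ 3, in any week.
- 6.3.2, contact and on-site dose: k ≥ 2 in the first week, k ≥ 7 afterwards.

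**Comparison.**

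| Period | k | 6.3.1 prompts a call | 6.3.2 requires contact and on-site dose |
|---|---|---|---|
| First week | 1 | no | no |
| First week | 2 | **no** | **yes** |
| First week | 3 or more | yes | yes |
| Later | 1 to 2 | no | no |
| Later | 3 to 6 | yes | no |
| Later | 7 or more | yes | yes |

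Only the row in bold has 6.3.2 demanding contact that 6.3.1 does not prompt. In later weeks, at 3 to 6 missed doses, 6.3.1 is the more cautious of the two, which is not a conflict.

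**Does the Week 1 visit close the gap?** Visit-day doses are taken on site, so a gap that runs up to the visit ends with an on-site dose anyway. Assume that the first week is Days 1 to 7, that Day 1 is dosed on site, and that the visit falls on Day 8 (inferred from the diary window for Week 1, Days 2 to 8, in SAP 8.A). A two-dose gap can then start on Day 2, 3, 4, 5 or 6, which gives 5 positions:

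- Days 2–3, 3–4, 4–5 and 5–6 missed: the next dose falls on Day 4, 5, 6 or 7, at home.
- Days 6–7 missed: the next dose falls on Day 8, on site.

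So 4 of 5 positions end in a home dose. SAP 4.E allows ±3 days for the visit, so Day 5 to Day 11. Leaving out gaps that would include the visit day itself:

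| Visit day | Positions ending in a home dose |
|---|---|
| 5 | 2 of 3 |
| 6 | 2 of 3 |
| 7 | 3 of 4 |
| 8 | 4 of 5 |
| 9, 10 or 11 | 5 of 5 |

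The visit catches some gaps and not others. These are counts of calendar positions, not probabilities; the documents give no frequency of missed doses.

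**The case against.** The strongest reply is that this is an omission and not a contradiction. Section 6.3.1 does not say that subjects should call only above 2, and its sentence on resuming the next day concerns a single forgotten dose. Section 6.3.2 is the more specific rule, binds subjects directly and comes immediately afterwards, so a site can follow both. Section 6.7 makes the investigator responsible for correct instruction. All of this stands, and it keeps the point small. It does not make the two thresholds agree: 6.3.1 is where the missed-dose counselling is written down, and in the first week its number is one too high.

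A second reply is that other text may already put this right. Section 10.5.7.4 is not visible, nor are the subject materials, and the summary-of-changes entry for 6.3.2 is partly redacted. That also stands. A reader might infer that subjects are in fact misinformed, or that the protocol lacks a first-week safeguard. The documents support neither: the safeguard is in 6.3.2, and what subjects are told in practice cannot be seen.

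A reader might also infer that monitoring is unconditionally required at 2 missed doses. Contact and the on-site dose are; monitoring is worded as something that should be done and/or discussed with the medical monitor.

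Finally, it is tempting to carry the point into the first week of the Open-Label Extension, because cardiac monitoring is repeated at Week 16 (9.2.5) and former placebo subjects may then be starting etrasimod. That depends on whether the first week of study treatment includes that week, which the visible text does not settle. Nor would the position counts carry over automatically, because the Week 16 and Week 17 visits each have their own ±3-day window.

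**Conclusion.** The inconsistency is real and confined to one value: exactly 2 consecutive missed doses in the first week of study treatment. There, 6.3.2 mandates contact and an on-site next dose, and 6.3.1 does not prompt the call. No visible text reconciles the two. Confidence in the threshold comparison is high, because it needs only the two sections and once-daily dosing. The view that the Week 1 visit does not reliably catch such gaps rests on the stated assumptions about visit day and the definition of the first week.

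It is a minor safety-text inconsistency, worth correcting because it touches a stated cardiac precaution and is cheap to remove. How often it would matter cannot be estimated from the documents. The extension question is separate and forms no part of this conclusion.

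**What to change.** Amend 6.3.1 so that, during the first week of study treatment, a subject who misses 2 or more consecutive doses is told to contact the investigator and not to take the next dose at home. A cross-reference to 6.3.2 would help. Keep the more-than-2 call rule for later weeks, where it already operates well before the 7-day threshold.

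The cost is one sentence in 6.3.1 and, if needed, a matching line in the subject instructions. It adds no visits or monitoring beyond what 6.3.2 already provides for.

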6.3.2. Dose Interruptions

If the investigator deems it necessary to withhold study treatment, temporary withholding is permitted for up to 3 days without obtaining prior approval from the Sponsor. If study treatment interruption ≥ 7 days is required for a medical reason, the investigator must contact the medical monitor as soon as this is anticipated.

The procedure for first-dose cardiac monitoring as outlined in Section 10.5.7.4 should be performed and/or discussed with the medical monitor any time a subject misses a study treatment as follows:

- ≥ 2 consecutive days within the first week of study treatment
- ≥ 7 consecutive days after the first week of study treatment

If these doses of study treatment are missed, subjects must contact the Investigator to discuss treatment re-initiation and are required to return to the study site before taking their next dose of study treatment. The subject must take the next dose of study treatment at the study site, and the in-clinic cardiac monitoring as outlined in Section 10.5.7.4 should be performed.

6.4. Method of Assigning Subjects to Treatment

For the Double-Blind Treatment Period, subjects will be centrally assigned to randomized study treatment using an Interactive Web Response System (IWRS). Details of the randomization methodology are provided in the statistical analysis plan (SAP).

During the Open-Label Extension Period, all eligible subjects will receive the same treatment (no randomization).

6.5. Selection and Timing of Dose for Each Subject

Subjects will self-administer 1 tablet once daily (with water, either with or without food). The tablet should be taken at approximately the same time each day, preferably in the morning. On visit days during the study, subjects should not apply any topical emollient or moisturizer prior to attending clinic and completing their visit. Additionally, on study visit days, subjects should wait and take their dose at the study site after blood draws [REDACTED] and after all pre-dose assessments have been completed.

6.6. Blinding

This study includes a Double-Blind Treatment Period with limited access to the randomization code. The investigational drug and placebo tablets are identical in physical appearance. The treatment each subject receives will not be disclosed to the investigator, study site staff, subject, Sponsor personnel involved with the conduct of the study (with the exception of the clinical supply staff and designated safety staff), or study vendors. The IWRS will hold treatment codes for study treatment.

The IWRS will be programmed with blind-breaking instructions. In the case of an emergency, the investigator has the sole responsibility for determining if unblinding of a subject's treatment assignment is warranted based upon medical necessity. Subject safety must always be the first consideration in making such a determination. If a subject's treatment assignment is unblinded, the medical monitor or Sponsor delegate must be notified within 24 hours after breaking the blind. The date and reason the blind was broken must be recorded in the source documentation and electronic case report form (eCRF), as applicable.

Unblinding may occur after all subjects have completed the Double-Blind Treatment Period, including the Safety Follow-Up Visit.

6.7. Treatment Compliance

The investigator is responsible for ensuring that subjects are correctly instructed on how to take their study treatment and that each subject is fully compliant with their assigned treatment regimen. Subject compliance will be based on tablet counts at specified study visits (Section 7.4 and Appendix 1; Table 8 and Table 9).

6.8. Concomitant Therapy

Any medication (including over-the-counter or prescription medicines, vitamins, and/or herbal supplements) or vaccine that a subject receives from Day 1 through the end of study must be recorded along with the following:

- Reason for use
- Dates of administration including start and end dates
- Dosage information including dose and frequency

The medical monitor should be contacted if there are any questions regarding concomitant therapy.

